### **3.1.2.2 Treatment Regimens and Dose-Escalation Rules Patients with FL and DLBCL until the Bridging cohorts**

[figure not shown]
During this first dose-escalation phase, patients will be enrolled according to the schema in [Figure 3](#). Three patients will initially be enrolled in each cohort, and up to 3 additional patients can be enrolled in a cohort at the Sponsor's discretion. The first patient in each cohort will be observed for safety for 1 week after Cycle 1 Day 1 before additional patients are enrolled in the same cohort. A minimum of 3 patients enrolled in a cohort must complete at least the first two cycles (i.e., the DLT assessment window, until Cycle 2, Day 28) before enrollment commences in the next cohort(s). Intra-patient dose escalation is not permitted in this study.

Enrollment will begin in a safety cohort in which patients will be treated at starting doses of 100 mg QD on Days 1–5 of each cycle for idasanutlin and 200 mg QD on Days 1–5 of each cycle for venetoclax, given in combination with obinutuzumab at the standard dose on Days 1, 8, and 15 of Cycle 1 and Day 1 of subsequent cycles (see [Figure 3](#) for details on treatment regimens). If treatment in the safety cohort is well tolerated, treatment will be initiated in Cohort 1 at the same doses as the safety cohort, except that patients will receive venetoclax on Days 1–10 of each cycle (see [Figure 3](#)). This regimen is referred to as Regimen A.

If the initial treatment regimen is not tolerated in the safety cohort, any subsequent cohorts will receive venetoclax on Days 1–5 of each cycle.

If safety and tolerability allow, the next two cohorts (Cohorts 2 and 3) will be enrolled concurrently. Patients in Cohort 2 will receive an escalated dose of venetoclax, while patients in Cohort 3 will receive an escalated dose of idasanutlin. Thus, only one drug will be escalated within each of the concurrent cohorts. If safety and tolerability allow, patients in Cohort 4 will receive both venetoclax and idasanutlin at the escalated doses given in the previous two cohorts (see [Figure 3](#)).

**Figure 3 Dose-Escalation Schema (Regimen A)**

Obinituzumab or rituximab are given at standard doses.

D1-5=Days 1-5; D1-10=Days 1-10; I=idasanutlin; QD = once a day; V=venetoclax.

If TLS is observed in the initial cohorts, venetoclax dosing may be modified as follows:

- Staggered dosing in which venetoclax may be initiated 2 or 3 days after the first idasanutlin dose during Cycle 1
- Initiation of Cycle 1 treatment below the target dose for venetoclax, followed by incremental dose increases until the target dose is achieved

During this first dose-escalation phase, study treatment will be administered as outlined in [Table 1](#)). Patients with FL who achieve a CR or a PR at the EOI will also receive maintenance treatment with obinutuzumab, venetoclax, and idasanutlin. Patients with DLBCL who achieve a CR or a PR at the EOI will also receive consolidation treatment with obinutuzumab, venetoclax, and idasanutlin. Post-induction treatment should start 8 weeks ( $\pm 1$  week) after Day 1 of the final cycle of induction and will continue until disease progression or unacceptable toxicity for up to 2 years for maintenance treatment and 6 months for consolidation treatment (see [Table 2](#)). Patients with DLBCL who achieve a CR based on modified Lugano 2014 criteria at the end of induction (defined as within 6-8 weeks after the start of the last cycle of study treatment) are allowed to proceed to hematopoietic stem cell transplantation if deemed appropriate by the investigator. Such patients will be followed for disease progression and survival. The dose and regimen for venetoclax and idasanutlin will be determined by the Sponsor upon review of all available safety, PK, PD, and efficacy data. The dose for maintenance/consolidation will not exceed the dose the patient received during induction. *The FL and DLBCL bridging cohorts may open at different times, and in this case, the venetoclax dosing regimen (5 vs. 10 days) may be explored independently.*

### **Combination of Rituximab, Idasanutlin, and Venetoclax in Patients with DLBCL in the Bridging Cohorts**

Following the identification of the MTDs for idasanutlin and venetoclax in combination with obinutuzumab, *or following Sponsor decision based on clinical judgment*, a bridging cohort of patients with DLBCL will be opened to *repeat the last dose tested* in combination with rituximab instead of obinutuzumab (375 mg/m^2 on Day 1 of each cycle; see [Figure 4](#) and [Table 1](#)).

If safety and tolerability allow, idasanutlin and venetoclax dose escalations may be explored in combination with rituximab in patients with DLBCL until identification of new MTDs (see [Figure 4](#)).

### **Combination of Obinutuzumab, Idasanutlin, and Venetoclax in Patients with FL in the Bridging Cohorts**

Following the identification of the MTDs for idasanutlin and venetoclax in combination with obinutuzumab in Regimen A, *or following Sponsor decision based on clinical judgment*, a bridging cohort of patients with FL will be opened to *repeat the last dose tested* in a different regimen. Obinutuzumab will be given alone in Cycle 1 and in combination with idasanutlin and venetoclax from Cycle 2 to 6 (see [Figure 4](#) and [Table 1](#)). This regimen is referred to as Regimen B.

If safety and tolerability allow, idasanutlin and venetoclax dose escalation may be explored with Regimen B in patients with FL until identification of new MTDs (see [Figure 4](#)).

After the last patient in each cohort has completed the two-cycle DLT observation period, the Sponsor, in consultation with the investigators, will evaluate the next dose recommended according to the mCRM (see [Section 3.1.2.3](#)) and agree on doses for the subsequent cohort(s), taking into account relevant demographic, adverse event, laboratory, dose administration, and PK (if available) data. At each dose-escalation step, the dose may be escalated or de-escalated, or an additional cohort at the same dose level may be enrolled.

[figure not shown]
On the basis of review of real-time safety data from this study and all available data from Study BH29812, dose escalation may be halted or modified by the Sponsor as deemed appropriate.

Although the DLT assessment window is defined as the first two treatment cycles, cumulative toxicities occurring beyond the first two cycles may be considered when determining the MTDs for idasanutlin or venetoclax.

Multiple MTDs may be identified, and the most appropriate RP2Ds will be chosen on the basis of safety, PK, and PD data. At the end of dose–escalation phase, RP2Ds (one for idasanutlin and one for venetoclax) in combination with obinutuzumab and one regimen will be decided for patients with FL. RP2Ds (one for idasanutlin and one for venetoclax) in combination with rituximab will be decided for patients with DLBCL. The RP2Ds of idasanutlin and venetoclax, as well as the treatment regimens for patients with FL and DLBCL, may be different.

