A Phase III study, BO21005, investigated G-CHOP compared with R-CHOP in patients with previously untreated DLBCL. The study did not meet its primary endpoint of PFS difference at final analysis. Based upon the BO21005 efficacy results, this study protocol has been amended (Version 3) to cease evaluating obinutuzumab in patients with R/R DLBCL in the expansion phase. Patients with DLBCL enrolled after the identification of idasanutlin and venetoclax maximum tolerated dose (MTD) in

combination with obinutuzumab will instead receive idasanutlin and venetoclax in combination with rituximab.

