## **3. STUDY DESIGN**

### **3.1 DESCRIPTION OF STUDY**

#### **3.1.1 Overview of Study**

This Phase Ib/II, open-label, multicenter, non-randomized, dose-escalation study will evaluate the safety, efficacy, and pharmacokinetics of obinutuzumab in combination with idasanutlin and venetoclax in patients with R/R FL and rituximab in combination with idasanutlin and venetoclax in patients with R/R DLBCL. The study will include an initial dose-escalation phase followed by an expansion phase. The dose-escalation phase is designed to determine the RP2Ds and regimen for idasanutlin and venetoclax in combination with obinutuzumab for FL patients and in combination with rituximab for DLBCL patients. Dose escalation starts with idasanutlin and venetoclax in combination with obinutuzumab in all patients (FL and DLBCL) until the MTD (Regimen A) *or until Sponsor decision based on clinical judgment* (see Section 3.1.2), followed by:

- Dose confirmation and potential dose escalation in patients with DLBCL for idasanutlin and venetoclax in combination with rituximab to determine the RP2Ds for this combination
- Dose confirmation and potential dose escalation in patients with FL with a different regimen (Regimen B, obinutuzumab given alone in Cycle 1 followed by idasanutlin, venetoclax, and obinutuzumab in combination in Cycles 2–6) to determine the RP2Ds for this regimen

The RP2Ds and regimen for FL and RP2Ds for DLBCL will be decided at the end of dose-escalation phase. Different RP2Ds and/or regimens may apply for FL and DLBCL, respectively.

[figure not shown]
In the expansion phase, patients with FL will receive idasanutlin and venetoclax at the RP2Ds of the selected regimen (Regimen A or B) in combination with obinutuzumab, and patients with DLBCL will receive idasanutlin and venetoclax at the RP2Ds in combination with rituximab (see Section 3.1.3).

Patients with R/R FL enrolled in the dose-escalation and expansion phases may be eligible to receive post-induction treatment (referred to as maintenance) with obinutuzumab, venetoclax, and idasanutlin (see Sections 3.1.2.2 and 3.1.3, respectively, for details on the treatment regimens).

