Cycles 1–6	
 
• Rituximab 375 mg/m^2 IV on Day 1
 
• Idasanutlin, oral Days 1–5, starting dose MTD identified in combination with obinutuzumab and venetoclax, minimal clinically and pharmacologically feasible dose-escalation steps 50 mg
 
• Venetoclax, oral, starting dose and regimen MTD identified in combination with obinutuzumab and idasanutlin, minimal clinically and pharmacologically feasible dose-escalation steps 100 mg
 
	

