**Table 1 Induction Treatment during the Dose-Escalation Phase for Patients with Follicular Lymphoma and DLBCL (cont.)**

Bridging Cohorts, Patients with Follicular Lymphoma Only (28-Day Cycles): Regimen B	
Cycle 1	
 
• Obinutuzumab 1000 mg IV on Days 1, 8, and 15
 

Cycle 2–6	
 
• Obinutuzumab 1000 mg IV on Day 1
 
• Idasanutlin, oral Days 1–5, starting dose MTD identified in combination with obinutuzumab and venetoclax, minimal clinically and pharmacologically feasible dose-escalation steps 50 mg
 
• Venetoclax, oral, starting dose and regimen MTD identified in combination with obinutuzumab and idasanutlin, minimal clinically and pharmacologically feasible dose-escalation steps 100 mg
 

DLBCL = diffuse large B-cell lymphoma; IV = intravenous; MTD = maximum tolerated dose; QD = once a day; TBD = to be determined.

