### 3.1.2.3 Use of Modified Continual Reassessment Model for Dose and MTD Determination

The dose escalation will employ a mCRM with overdose control design in order to define the MTD and/or the recommended dose for subsequent cohorts.

The design is based on the primary safety variable, that is, the occurrence of a DLT. The MTD is defined as the dose that maximizes the probability of achieving a DLT rate of 16%–33% (target toxicity interval) and results in a <35% probability of having a DLT rate of >33% (overdose control).

The maximum allowable increments for idasanutlin from the highest dose already tested will not exceed 100 mg, with a minimum increase of 50 mg. The maximum allowable increments for venetoclax from the highest dose already tested will not exceed 200 mg, with a minimum increase of 100 mg.

In addition, the dose of idasanutlin will not be escalated above 600 mg and the dose of venetoclax will not be escalated above 800 mg. The selection of the next dose will be subject to clinical judgment and mandated safety constraints that limit the size of the dose increments. Clinical judgment will always override mCRM recommendations in the dose-selection process.

A detailed algorithm for the selection of the next recommended combination of doses in the dose-escalation procedure is described in [Appendix 6](#). As stated above, only combinations of doses with a <35% probability of having a DLT rate of >33% will be allowed.

Dose escalation will stop when the maximum allowed sample size, 60 patients, has been reached or there is enough confidence in the prediction of the MTD (e.g., at least 6 patients have been recruited at the MTD doses and there is a >40% probability of having a DLT rate of 16%–33%).

The following two marginal models (two-parameter logistic regression), which describe the relationship between DLT and idasanutlin dose in the absence of venetoclax, and conversely, the relationship between DLT and venetoclax dose in the absence of idasanutlin, were considered:

$$\text{logit}\left(p(d_{IDA,i}^*)\right) = \alpha_1 + \beta_1 \log(d_{IDA,i}^*) \quad (1)$$

$$\text{logit}\left(q(d_{VEN,i}^*)\right) = \alpha_2 + \beta_2 \log(d_{VEN,i}^*) \quad (2)$$

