## **4.2 METHOD OF TREATMENT ASSIGNMENT**

This is a Phase Ib/II, open-label, multicenter, non-randomized study of obinutuzumab in combination with idasanutlin and venetoclax in patients with R/R FL and obinutuzumab or rituximab in combination with idasanutlin and venetoclax in patients with R/R DLBCL. Following determination of the MTDs with idasanutlin and venetoclax in combination with obinutuzumab, cohort(s) of patients with DLBCL will be opened to confirm the MTDs of idasanutlin and venetoclax in combination with rituximab. Following determination of the MTDs of idasanutlin and venetoclax in combination with obinutuzumab, cohort(s) of patients with FL will be opened to explore a different regimen (Regimen B, obinutuzumab alone at Cycle 1 and obinutuzumab in combination with idasanutlin and venetoclax at Cycles 2–6). During the dose-escalation phase, patients will be assigned to dosing groups through use of an interactive voice or Web-based response system (IxRS). During the expansion phase, all patients will be assigned to receive the RP2Ds with the selected regimen via IxRS. If eligible, patients will receive maintenance (FL patients) or consolidation (DLBCL patients) treatment (see Sections 3.1.2 and 3.1.3 for details).

Enrollment tracking will be performed through use of the IxRS. Prior to initiation of screening, study site personnel should confirm through the appropriate communication channel that the planned dose-escalation or expansion cohort is open for enrollment. After written informed consent has been obtained and preliminary eligibility has been established, the study site will submit documentation supporting eligibility to the Sponsor and obtain the Sponsor's approval to enroll the patient. Once the Sponsor reviews and approves a patient for enrollment, a patient number will be assigned and the patient will be enrolled via the IxRS. The Sponsor will communicate to the sites impending closure of screening for a particular disease cohort.

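### Section 3.1.2.2 starts both bridging cohorts at the last dose tested, Table 1 starts them at the MTD, and the two doses can differ

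*Protocol*

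**What the plan says.** Three parts of the current protocol (Version 4) govern the start of the bridging cohorts.

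- **Section 3.1.2.2**, in separate paragraphs for DLBCL and FL, opens each cohort once the MTDs with obinutuzumab are identified or when the Sponsor so decides on clinical judgment. The purpose in both paragraphs is to "repeat the last dose tested", with rituximab for DLBCL and in Regimen B for FL. Both refer to Table 1 and Figure 4.
- **Table 1**, in both bridging panels, sets idasanutlin at "starting dose MTD identified in combination with obinutuzumab and venetoclax" and venetoclax at "starting dose and regimen MTD identified in combination with obinutuzumab and idasanutlin".
- **Section 4.2** says for FL: "Following determination of the MTDs of idasanutlin and venetoclax in combination with obinutuzumab, cohort(s) of patients with FL will be opened". For DLBCL, after the same trigger, cohorts "will be opened to confirm the MTDs of idasanutlin and venetoclax in combination with rituximab". It does not mention the Sponsor-decision route, although Section 3.1.1 does.

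Section 3.1.2.3 supplies the overdose limit: "only combinations of doses with a <35% probability of having a DLT rate of >33% will be allowed". It also says that clinical judgment overrides the model, and it gives its stopping rule (at least 6 patients at the MTD doses and more than 40% probability of a DLT rate of 16%–33%) only as an example.

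**The concern.** The last dose tested and the MTD are different things. The last dose tested is a fact about enrolment. The MTD is a model result that uses that cohort's DLTs, so a dose that was admissible when it was given can be inadmissible once its results are in. Section 3.1.2.2 also allows de-escalation, and it enrols Cohorts 2 and 3 concurrently, so the last dose tested may not even name a single combination.

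On the Sponsor-decision route there may be no MTD. Table 1 then gives no start dose, and the text of Section 3.1.2.2 is the only rule.

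The bridging cohorts set the RP2D for DLBCL and may set it for FL. They are also the first exposure to a new antibody combination or schedule. The start dose should follow one rule, and that rule should not be able to name a combination that the protocol's own limit excludes.

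**Working it through.** **Aim.** To see whether the two rules can name different doses under the protocol's own model. The plan states no figure for this, so there is none to reproduce.

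**Inputs (Section 3.1.2.3).** Doses are idasanutlin/venetoclax in mg, with x = idasanutlin/200 and y = venetoclax/400.
- Marginal models: logit p = α₁ + β₁ log x and logit q = α₂ + β₂ log y.
- No interaction: π⁰ = p + q − pq. With interaction: odds(π) = odds(π⁰) · exp(γxy).
- Priors: (α₁, log β₁) has means (−2.0, 0.916), variances 1.665 and 0.002, covariance 0.037. (α₂, log β₂) has means (−3.905, 1.685), variances 1.47 and 0.003, covariance 0.0299. log γ ~ N(0.4, 1.0).
- Limit: P(π > 0.33) < 0.35.
- Cohort order from Section 3.1.2.2: Cohort 1 at 100/200, Cohorts 2 and 3 each raising one drug, Cohort 4 raising both. I took the largest permitted steps, 200 mg for venetoclax and 100 mg for idasanutlin. The Days 1–5 safety cohort is left out, because Section 3.1.2.3 models the two venetoclax schedules separately by default.

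**Method.** Prior draws (at least one million) weighted by the binomial likelihood; Monte Carlo error about 0.001.

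**Planned order.** 0/3 DLTs at each of 100/200, 100/400 and 200/200, then 200/400.

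| Data at 200/400 | P(π > 0.33) at 200/400 | Meets < 0.35? |
|---|---|---|
| None yet | 0.31 | Yes |
| 1/3 DLTs | 0.32 | Yes |
| 2/3 DLTs | 0.66 | No |
| 3/3 DLTs | 0.91 | No |

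After 2/3 DLTs, 150/400 has P(π > 0.33) = 0.23 and is allowed. Just before the cohort is treated, the model's own predictive probability of at least 2/3 DLTs at 200/400 is 0.22, so the case is not remote. If bridging opened at that point, Section 3.1.2.2 read literally would start at 200/400, which fails the limit.

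**Sensitivity.**
- Adding the six Study BH29812 patients of Section 1.3.2 (three each at 100 and 150 mg idasanutlin, no venetoclax) as 0 DLTs gives 0.64 at 200/400, 0.22 at 150/400 and a predictive probability of 0.20. This assumes a comparable DLT definition.
- With smaller steps, no DLTs in the first three cohorts and 2/3 at the last, the last dose has 0.53 at 200/300, 0.49 at 150/400 and 0.36 at 150/300. The last of these is borderline and passes at 0.33 when BH29812 is added.

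**When the rules agree.** Suppose that after 2/3 DLTs at 200/400 the Sponsor de-escalates and sees 1/6 at 150/400. Then 150/400 has P(π > 0.33) = 0.12 and P(0.16 ≤ π ≤ 0.33) = 0.55, with 6 patients, so the example stopping rule is met. The last dose tested is the MTD, and both rules give 150/400.

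**Same data, different order.** The posterior does not depend on order. If the 150/400 patients come before the 200/400 cohort, 150/400 still meets the example stopping rule, but the last dose tested is 200/400 with P(π > 0.33) = 0.60. The two rules then disagree although an MTD exists. That order departs from the sequence in Section 3.1.2.2, which goes straight from Cohorts 2 and 3 to both escalated doses.

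**The case against.** The strongest reply is that the protocol, read as a whole, obliges nobody to start at a failing dose. Section 3.1.2.3 allows only combinations within the limit and lets clinical judgment override. Section 3.1.2.2 requires a dose review after each cohort and permits de-escalation. Section 4.2 has the Sponsor approve each enrolment. The example stopping rule also tends to bring the last dose and the MTD together. All of this stands and limits the practical risk. It does not settle which start rule applies, because the stopping rule is only an example and the early route needs no MTD.

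A second reply is that the probabilities above describe Regimen A. Section 3.1.2.3 provides a similar but unspecified model for the bridging regimens. Section 3.3.2.1 introduces Regimen B to ease Cycle 1 haematologic toxicity and expects less overlapping toxicity with rituximab, so repeating a dose that was limiting in Regimen A might be deliberate. This also stands: the figures show that the rules can diverge, not what toxicity to expect in bridging. If repeating such a dose is the intention, the protocol should say so, and Table 1 says otherwise.

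Two stronger readings go too far. A reader might infer that Section 4.2 forbids early opening; it names one trigger but does not exclude others. A reader might also infer that the plan builds in overdosing. Failing the limit is not proof of excess toxicity: with the Appendix 6 parameters and γ = 1, the true DLT rate at 200/400 is 0.30, inside the 16%–33% target.

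I could not see Figure 4. It may state a start dose, but it cannot remove the difference between the text and Table 1.

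**Conclusion.** The conflict is real and lies in the current text. Section 3.1.2.2 and Table 1 give different start rules for both bridging cohorts, and Section 4.2 omits the Sponsor-decision route. A likely cause is that the Version 4 change reached Sections 3.1.1 and 3.1.2.2 but not Table 1 or Section 4.2.

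The rules can name different doses: in the planned order, two DLTs in three patients at 200/400 put the last dose at 0.66 against a limit of 0.35, while 150/400 stands at 0.23. They coincide if escalation continues at a lower dose until an MTD is declared there. They part when bridging opens before that, or when cohorts are taken out of the planned order.

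This is a rule conflict with a modest safety aspect, and it should be fixed. The size rests on the stated priors, the Regimen A model, the largest permitted dose steps and the illustrative DLT counts. How often the rules would diverge in practice is not estimated here.

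**What to change.** 1. **MTD identified.** In both bridging paragraphs of Section 3.1.2.2, replace the instruction to repeat the last dose with: start at the MTD identified in Regimen A (if more than one, the combination chosen by the Sponsor). This matches Table 1.
2. **Early opening by Sponsor decision.** State in Section 3.1.2.2, both bridging panels of Table 1 and Section 4.2: start at a tested combination that has completed the DLT window and meets the Section 3.1.2.3 overdose criterion on the Regimen A data then available.
3. Add the Sponsor-decision route to Section 4.2, and check that Figure 4 agrees.

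The first change is wording only. The second is a small design decision, because it makes the Regimen A data the basis for the early start. The cost is a slightly lower start in some cases, which matters if rituximab or Regimen B proves milder. It can be recovered through the bridging escalation that Section 3.1.2.2 already allows.
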